**Figure 1: Study Design**

Abbreviations: DBPCFC = Double-blind, placebo-controlled food challenge; EPIT = Epicutaneous immunotherapy; IgE = Immunoglobulin E; pp = peanut protein; SPT = Skin prick test.

The schedule of procedures is presented in [table 1](#).

 Open-label Follow-up Study of the PEPITES Study to Evaluate the Long-term Efficacy and Safety of Viaskin® Peanut

Table 1: Schedule of Procedures

Study Assessments	Screening			Treatment Period												End of Study		Early Termination	Unscheduled Visit					
	V1	V2	V3 	V4 	PC	V5	PC	D22	M1	M2	M3	PC	M4.5	M6	M7.5	M9	M12			V10	V11	V12	ET	UV 
	D-42			D1	D4	D8																		
Informed consent	X																							
Eligibility (inclusion/exclusion criteria)	X 			X																				
Medical history 	X																							
Parental medical history of atopy	X																							
Demographics	X																							
Physical examination 	X	X 		X				X	X					X	X			X 	X 	X		X	X	X
Vital signs 	X	X 		X				X	X					X	X			X 	X 	X		X	X	X
Spirometry (FEV 1 ) 	X													X	X			X	X			X	X	X
PEF	X	X 		X				X	X					X	X			X 	X 	X		X	X	X
SCORAD	X													X	X			X	X					
Skin Prick Test	X													X	X			X	X			X		
Immunological markers 	X													X	X			X	X			X		
Laboratory tests 	X													X	X			X	X			X		X
FAQLQ/FAIM 	X																	X	X					
Filaggrin gene: informed consent - blood sampling														X 	X 			X 	X 					
Pregnancy test	X																	X	X			X		
Epigenetic analyses	X													X	X			X	X					
DBPCFC		X	X															X	X					
Randomization				X																				
Adverse events	X	X	X	X	X	X	X	X	X	X	X	X	X	X	X	X	X	X	X	X	X	X	X	X
Concomitant medications	X	X	X	X	X	X	X	X	X	X	X	X	X	X	X	X	X	X	X	X	X	X	X	X

CCI

CONFIDENTIAL

Project Document Version No. 3.0

Project Document Effective Date: 04-Oct-2017

Study Assessments	Screening			Treatment Period														End of Study		Early Termination	Unscheduled Visit			
	V1	V2	V3 	V4 	PC	V5	PC	D22	M1	M2	PC	M3	M4.5	PC	M6	M7.5	M9	V9	V10	V11	V12	ET	UV 	
	D-42			D1	D4	D8																		
Check for accidental peanut consumption						X	X	X	X	X					X	X	X	X			X		X	
Subject diary (dispense/check)				X	X	X	X	X	X						X	X	X	X			X		X	
Dispense subject safety leaflet and subject identification card				X																				
Study drug dispensation				X					X						X									
Apply 1 Viaskin® patch at site				X																				
Check the used/unused study drug dispensed						X			X						X						X		X	
Check skin reaction under the patch and grade it 				X		X			X						X						X		X	
Photographs of the back where patches were applied				X		X			X						X						X		X	
Patch adhesion: - subject's assessment												X 	X 	X 	X 	X 	X 	X 	X 					
Patch adhesion: - Investigator's assessment				X		X			X						X						X			
Dispense epinephrine auto-injector and anaphylaxis emergency action plan				X																				
Review utilization of epinephrine auto-injector						X			X						X									

Study Assessments	Screening		Treatment Period												End of Study		Early Termination	Unscheduled Visit		
	V1	V2	V3 	V4 	PC	V5	PC	V6	PC	V7	PC	V8	PC	V9	V10	V11	V12	ET	UV 	
	D-42			D1	D4	D8	D22	M1	M2	M3	M4.5	M6	M7.5	M9	M12					
and anaphylaxis emergency action plan (when required)																				
Hours under observation before discharge		3	3	3											3	3				

Abbreviations: D = Day; DBPCFC = Double-blind, placebo-controlled food challenge; ET = Early termination; FAQLQ/FAIM = Food Allergy Quality of Life Questionnaire/Food Allergy Independent Measure; FEV1 = Forced expiratory volume in one second; M = Month; PC = Phone contact; PEF = Peak expiratory flow; SCORAD = Scoring atopic dermatitis; SPT = Skin prick test; UV = Unscheduled Visit; V = Visit.

- 1 Visit 3 within 2 weeks of V2 and through D-1. Visit 4 may take place on the same day as Visit 3, but this would result in a very long day for the subject (parents/guardians) as all Visit 4 procedures would then have to take place that same day.
- 2 Unscheduled Visit in case of AEs, need for treatment re-supply, etc. Procedures will be performed as deemed necessary by the investigator.
- 3 Except for those that depend on the results of the immunological markers testing (peanut-specific IgE) and on the outcome of the entry/screening DBPCFC.
- 4 Including history of peanut allergy.
- 5 Including a complete skin examination, body weight and height.
- 6 These examinations are to be done before the DBPCFC. Additionally, they can be repeated during the DBPCFC procedure on both days anytime if judged necessary by the Investigator.
- 7 Blood pressure, heart rate and respiratory rate.
- 8 FEV1 will be measured in subjects 6 years of age and older.
- 9 Peanut-specific IgE, peanut-specific IgG4, peanut specific IgE and peanut specific IgG4 to Ara h 1, Ara h 2, Ara h 3, Ara h 8 and Ara h 9. IgE specific to cow's milk, egg white, house dust mites, and grass pollen will be collected at Visit 1 and Visit 10 only and in case of an early termination visit.
- 10 Laboratory tests performed centrally. Hematology: hemoglobin, hematocrit, platelets, red blood cells, white blood cells with differential cell count. Biochemistry: aspartate aminotransferase, alanine aminotransferase, total bilirubin, total protein, blood urea nitrogen, creatinine.
- 11 For both FAQLQ and FAIM, subjects ≥8 years of age will use the Child Form of the FAQLQ/FAIM. All parents/guardians will use the Parental Form for children. The specific forms of FAQLQ and FAIM will be completed in the countries where they are available in local languages.
- 12 Signing the consent for the flagrin genetic analysis can be done any time after the subject is effectively randomized in the study. However, collection of blood is recommended only once at any of the following visits: Visit 7, 8 or 10.
- 13 Check the reaction of the skin on the back of the subject and grade the severity of the local skin reactions. At Visit 4, grading is to be done before patch

- application and 30 min, 1 h, 2 h and 3 h after patch application.
- 14 The assessment of the patch adhesion to the skin will consist of a 28-day specific analysis to occur between Month 3 (Visit 7) and Month 6 (Visit 8). This assessment period can be extended up to Month 9 (Visit 9) in case it has not been completed or fully completed between Month 3 and Month 6.
  - 15 The same treatment box dispensed at visit 9 will be re-dispensed at visit 10 (until visit 11) after the compliance has been assessed

Time windows:

Visit	Time windows
V1	D-42 max before V4
V2	Anytime through D-2
V3	Within 1 weeks of V2 and through D-1
PC-D4, PC-D22	+/- 2 days
V5 (D8), V6 (M1), PC-M2	+/- 3 days
V7 to V10 (M3,6,9,12,PC M4.5, M7.5)	+/- 7 days
V11	Maximum 1 week after V10
V12	V11 + 2 weeks

### 3.2 Efficacy and Safety Endpoints

The DBPCFC to peanut will be performed at study entry and at Month 12 in order to assess the primary efficacy endpoint and the secondary efficacy endpoints.

#### Primary efficacy endpoint:

The primary efficacy endpoint is the difference between percentage of treatment responders in the active Viaskin® Peanut 250 µg group compared to the placebo group after 12 months of EPIT treatment in the overall population. A subject is defined as a treatment responder if:

- The initial ED was >10 mg peanut protein and the ED is  $\geq 1,000$  mg peanut protein at the Month 12 DBPCFC, or;
- The initial ED was  $\leq 10$  mg and the ED is  $\geq 300$  mg peanut protein at the Month 12 DBPCFC.

To ensure the validity of this endpoint, the actual screening ED value entered in the eCRF will be used to define the initial ED. This will account for any randomization stratum error. Additionally, actual screening ED value entered in the eCRF will be used to define screening ED subgroups (screening ED  $\leq 10$  mg / screening ED  $> 10$  mg). Alternatively, the screening ED value used for the randomization (that may include randomization stratum errors), is designated hereunder as “Screening ED stratum”.

#### Secondary efficacy endpoints:

The following secondary efficacy endpoints will be analysed.

- Percentage of treatment responders at Month 12 in the active Viaskin® Peanut 250 µg group compared to the placebo group in each of the 2 screening ED subgroups.
- Percentage of treatment responders at Month 12 in the active Viaskin® Peanut 250 µg group compared to the placebo group in each of the 2 age subgroups: 4 to 5 years-old; 6 to 11 years-old.
- Mean and median cumulative reactive dose of peanut protein and change from Baseline at Month 12 in the active Viaskin® Peanut 250 µg group versus the placebo group in the overall population, and for each screening ED subgroup.
- Mean and median ED of peanut protein and change from Baseline at Month 12 in the active Viaskin® Peanut 250 µg group versus the placebo group in the overall population, and for each screening ED subgroup.
- Percentage of subjects responsive (those showing objective symptoms leading to DBPCFC stop) to a cumulative dose  $\geq 1,444$  mg peanut protein at the Month 12 DBPCFC in the active Viaskin® Peanut 250 µg group versus the placebo group in the overall population, and for each screening ED subgroup.
- Percentage of subjects unresponsive (those showing no objective symptoms leading to DBPCFC stop) to a cumulative dose  $\geq 1,444$  mg peanut protein at the

Month 12 DBPCFC in the active Viaskin® Peanut 250 µg group versus the placebo group in the overall population, and for each screening ED subgroup.

- Percentage of subjects unresponsive (those showing no objective symptoms leading to DBPCFC stop) to the highest dose of peanut protein, which is the percentage of subjects who pass the Month 12 DBPCFC in the active Viaskin® Peanut 250 µg group versus the placebo group in the overall population, and for each screening ED subgroup.

### **Other efficacy endpoints:**

The following variables will also be analysed:

- Change from baseline in peanut-specific IgE and IgG4 at months 3, 6 and 12 in the active Viaskin® Peanut 250 µg group versus the placebo group in the overall population, and for each screening ED subgroup;
- Change from baseline in peanut skin prick testing average wheal diameters at months 3, 6 and 12 in the active Viaskin® Peanut 250 µg group versus the placebo group in the overall population, and for each screening ED subgroup;
- Quality of life scores (Food Allergy Quality of Life Questionnaire [FAQLQ]/Food Allergy Independent Measure [FAIM]) at Baseline and Month 12 and change from baseline in FAQLQ score at Month 12 in the overall population.

### **Criteria for Evaluation of Study Drug Safety**

The following safety criteria will be evaluated:

- AEs and treatment-emergent adverse events (TEAEs) by System Organ Class (SOC) and Preferred Terms (PTs);
- TEAEs by maximum severity and relatedness to Viaskin® Peanut 250 µg;
- Incidence, duration and maximum severity of local cutaneous Viaskin® Peanut 250 µg-induced AEs as assessed by the subject;
- Severity of local cutaneous Viaskin® Peanut 250 µg-induced AEs as assessed by the Investigator;
- Adverse events of special interest (AESI) including grade 4 local cutaneous reactions and systemic allergic AEs considered related to Viaskin® Peanut 250 µg;
- Serious adverse events (SAEs) by SOC and PTs, and relatedness to Viaskin® Peanut 250 µg (SAEs due to DBPCFC will be presented separately);
- Laboratory data, physical examinations and vital signs;
- Spirometry results and PEF results.

The above criteria will be studied overall and by treatment group, in the Safety population, as well as for the age ranges 4 to 5 years, 6 to 8 years and 9 to 11 years, and for each screening ED subgroup.

## Criteria for Evaluation of Study Procedure Safety

- Objective symptoms elicited during the entry/screening DBPCFC and Month 12 DBPCFC by severity;
- Change in severity of objective symptoms elicited during the DBPCFC from Baseline to Month 12 in the active Viaskin® Peanut 250 µg group versus the placebo group;
- SAEs elicited during the entry/screening DBPCFC and Month 12 DBPCFC.

The above criteria will be studied overall and by treatment group, in the Safety population, as well as for the age ranges 4 to 5 years, 6 to 8 years and 9 to 11 years, and for each of the screening ED subgroup.

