#### 4.2 Exclusion Criteria

Subjects will be enrolled in this study only if they meet none of the following criteria:

1. History of severe anaphylaxis to peanut with any of the following symptoms: hypotension, hypoxia, neurological compromise (collapse, loss of consciousness or incontinence);
2. Pregnancy or lactation;
3. Severe reaction during the entry/screening DBPCFC, defined as need for intubation, hypotension persisting after epinephrine administration, and/or the need for  $\geq 3$  doses of epinephrine;
4. Objective IgE-mediated symptoms to the placebo formula during the entry/screening DBPCFC and leading to stopping the challenge;
5. Viral upper respiratory infection or gastroenteritis within 7 days of a food challenge (challenge must be rescheduled to occur at least 7 days after recovery);
6. Any clinically significant abnormality identified at the time of screening such as major infectious diseases (for example chicken pox, measles) which in the judgment of the Investigator may preclude safe participation or strict compliance with the protocol procedures (subjects can be considered for the study after recovery from these diseases);
7. Generalized dermatologic disease (for example active atopic dermatitis, uncontrolled generalized active eczema, ichthyosis vulgaris) extending widely on the skin and especially on the back with no intact zones to apply the Viaskin® patches;
8. Symptomatic seasonal allergies that may interfere with the conduct of a DBPCFC. Subjects should be screened at a time when such allergies are asymptomatic (for example outside of the culprit season);
9. Known hypersensitivity to any of the Viaskin® patch components (except peanut), including the adhesive film;
10. Known hypersensitivity to any component of the food challenge formula (except peanut);
11. Inability to discontinue short-acting antihistamines or long-acting antihistamines for the minimum wash-out periods as specified in the table in [APPENDIX 4](#)) prior to the skin prick testings or the food challenges;
12. Spirometry forced expiratory volume in 1 second ( $FEV_1$ )  $< 80\%$  of the predicted value at screening (visit 1) for subjects  $\geq 6$  years of age and able to perform the spirometry, or PEF  $< 80\%$  of predicted value at screening (visit 1) for subjects performing only the PEF measurements.
13. Diagnosis of asthma that fulfills any of the following criteria:

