### 4.5.3 Allocation/Randomization of Patients to Treatment

Randomization of subjects to treatment will occur at Visit 4 after all screening procedures have been performed and eligibility for the study confirmed. Each randomized subject will be assigned by the IWRS a kit number based on a pre-defined algorithm/pre-defined randomization list.

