#### 4.4.5 Safety Population

The safety population will be comprised of all subjects who are randomized and have received at least one dose of study drug. This population will be used to assess comparative safety information. In case the wrong study drug is dispensed, the subject will be analyzed according to the study drug received for the longest period of time. In the event that a subject is stratified incorrectly, ‘actual’ screening ED value will be used rather than ‘randomized stratum’.

A subject is assumed to have received at least one dose of study drug:

- If the date/time of first dose is completed in the eCRF
- Or if at least one patch adhesion scoring is completed (in case the date of first dose is missing)

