#### 4.9 Study Drug Safety Evaluation

The safety analysis will be run on the safety population, successively on the following set of subjects:

- For all subjects
- For the subjects within the age range 4 to 5 years: 4 to 6 years old (6 years excluded)
- For the subjects within the age range 6 to 8 years: 6 to 9 years old (9 excluded)
- For the subjects within the age range 9 to 11 years: 9 to 12 years old (12 excluded)
- For each ED screening subgroup

Some safety sub-analyses will be also run on subjects with mutations in the filaggrin gene versus subjects carrying the wild type gene.

Results will be presented by treatment group and overall.

Unless specified no missing data will be replaced/imputed (see Section 4.9.1).

Symptoms due to DBPCFC will be reported in specific pages of the eCRF and not in the AE form, unless the reaction is serious. SAEs due to DBPCFC will be presented separately from AEs (see [Section 4.9.10](#)) and will be excluded from all tables and listings summarizing AEs/TEAEs.

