All SAEs elicited during the entry/screening DBPCFC and Month 12 DBPCFC will be tabulated by SOC and PT and will also be listed.

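### Entry-challenge safety is tabulated in the Safety population, so children barred by exclusion 3 for a severe entry reaction are absent by construction, while the same reactions at Month 12 are counted

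*SAP*

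**What the plan says.** SAP 3.2 names three criteria for procedure safety: objective symptoms by severity at both challenges, change in their severity, and "SAEs elicited during the entry/screening DBPCFC and Month 12 DBPCFC". One sentence then sets the population for all three: "The above criteria will be studied overall and by treatment group, in the Safety population". SAP 4.9, the parent of the section on challenge reactions, opens with the same rule: "The safety analysis will be run on the safety population, successively on the following set of subjects". SAP 4.6 tabulates antihistamine and epinephrine intakes during challenges and summarizes medications for the Safety population.

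SAP 4.4.5 defines that population: "The safety population will be comprised of all subjects who are randomized and have received at least one dose of study drug". Protocol 4.5.3 fixes the timing: "Randomization of subjects to treatment will occur at Visit 4 after all screening procedures have been performed and eligibility for the study confirmed". Exclusion 3 in Protocol 4.2 reads "Severe reaction during the entry/screening DBPCFC, defined as need for intubation, hypotension persisting after epinephrine administration, and/or the need for" three or more doses of epinephrine.

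SAP 4.9.10 adds that "All SAEs elicited during the entry/screening DBPCFC and Month 12 DBPCFC will be tabulated by SOC and PT and will also be listed", without naming a population. SAP 4.9 says that challenge SAEs are presented separately and "will be excluded from all tables and listings summarizing AEs/TEAEs". SAP 4.4.1 defines a Screened population, but the SAP text assigns no challenge-safety output to it.

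**The concern.** The challenge is a study procedure with its own safety criteria, and Protocol 3.3 acknowledges that it can provoke severe reactions. Earlier studies bear this out: 14 of the 20 SAEs in the Phase IIb VIPES study were related to the challenge (Protocol 1.1.1.2.3), and 5 of the 20 SAEs in the ARACHILD pilot were attributed to the study procedure and occurred during it (Protocol 1.1.1.2.2).

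An entry table that cannot contain the protocol's own category of severe entry reaction is an incomplete account of that procedure. A reader who sees none at entry could take this as evidence of safety when it follows from who was allowed into the table. If some of these events then appear at Month 12, setting the two columns side by side suggests a change that may reflect selection.

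**Working it through.** **1. Who can be in the entry tables.**
- The entry challenge takes place at Visits 2 and 3 (Protocol 7.2.2 and 7.2.3), and randomization follows at Visit 4.
- A child who meets exclusion 3 at Visit 2 or 3 should not be randomized, so is not in the Safety population. Only an eligibility violation could put such a child there.
- The expected count of exclusion 3 reactions in the entry tables is therefore 0, apart from violations. No event rate is needed for this.
- Entry epinephrine counts are likewise cut off at 2 doses by eligibility.
- Protocol 6.1.1.4 and the SAP contain no matching removal at Month 12.

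**2. Whether another planned output recovers these children.**
- General AE and TEAE tables and listings: no, because challenge SAEs are taken out of them (SAP 4.9).
- Listing of reasons for non-randomization (SAP 4.3.1): it should show that a child was barred, but not the symptoms, grades or treatment.
- SAE table and listing in SAP 4.9.10: the sentence says all, but it names no wider population and sits under the rules in SAP 3.2 and 4.9.
- Even a wide reading of that sentence covers SAEs only. Protocol 6.2.1.3.6 keeps challenge symptoms on the challenge pages and ties a challenge SAE to anaphylaxis needing at least an overnight stay. A child given three epinephrine doses and discharged the same day may therefore appear only on those pages.

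**3. How many children could be affected.** The plan gives 330 randomized and up to 30% screen failure (Protocol 8.10, SAP 4.12).
- Number screened: 330 / (1 − 0.30) = 471.4, which agrees with the stated figure of about 470.
- Screened but not randomized: 470 − 330 = 140, and 140 / 470 = 29.8%.

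The 140 is a ceiling on children, not a count of reactions. Under Protocol 7.2.2, Visit 2 goes ahead only once the inclusion criteria, including peanut-specific IgE, are met, so some screen failures are never challenged. Others take the challenge and do not react.

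The documents give neither the number challenged nor a rate for exclusion 3 reactions. Assuming, purely for illustration, rates of 0.5% to 5% of challenged children:
- Low end, where the only challenged children not randomized are those barred by exclusion 3: 330 × 0.005 / 0.995 = 1.7.
- High end, where all 470 are challenged: 470 × 0.05 = 23.5.

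A range this wide, resting on rates with no source in the documents, is no basis for quoting a size.

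**4. Which way the entry-to-Month 12 reading is shifted.** Eligibility trims the entry data at both ends:

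| Feature | Entry, Safety population | Month 12 |
|---|---|---|
| Exclusion 3 reactions | removed | kept |
| Children with no objective reaction | removed (Protocol 6.1.1.3) | kept |
| Top challenge dose (Protocol 6.1.1.2) | 300 mg | 2,000 mg |

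For counts of exclusion 3 events, the first row works in one direction only: entry is held at 0 and Month 12 is not. For the severity score, the first and second rows work against each other and the third differs as well, so the net sign is unknown.

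**5. Whether the arms are affected differently.** The selection happens before randomization and applies equally to both arms. Excluded children have no Month 12 challenge and cannot contribute to a change score. The by-arm comparison of change is not biased by this rule.

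**The case against.** The other side has several fair points.

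The SAE sentence in SAP 4.9.10 is unrestricted on its face, and the index of tables and listings is in a separate document (SAP Appendix 4), so a listing for all screened children may be intended. That possibility stands. As written, however, two explicit population rules govern the section, and a programmer who follows them would leave these children out.

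Tables by arm on randomized, dosed children are conventional, and a child who was never randomized has no arm. This is correct for Month 12 and for change. It is no reason to restrict an account of a procedure that takes place before randomization.

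The events also do not go unseen during the trial. Screening SAEs are recorded in the e-CRF and must be reported within 24 hours (Protocol 6.2.1.4 and 6.2.1.5), and a DSMB reviews safety data. This is relevant to oversight but does not supply the missing table.

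A reader might also infer that all the worst entry reactions vanish, or that the study report would hold no trace of the barred children. The documents do not support either. Exclusion 3 is narrow: children with grade 3 symptoms or an overnight-stay SAE who do not meet it can be randomized and do appear. The listing of reasons for non-randomization should also identify those who were barred.

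**Conclusion.** The point holds as a fault in a stated rule. Under SAP 3.2, 4.6 and 4.9, the entry-challenge safety tables contain no reactions meeting exclusion 3 except through eligibility violations, while the same reactions at Month 12 are counted. The result is an incomplete account of entry-challenge safety, and raw entry and Month 12 counts of these events that should not be compared directly. This rests on the population definitions and the timing of randomization, and on no assumed rate.

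Three stronger readings are tempting and should not be drawn:
- That the severity score is tilted toward a worse Month 12. Non-reactors are also removed at entry and the top dose differs, so the direction is not established.
- That the treatment comparison is biased. The selection precedes randomization and is the same in both arms.
- That 140 children, or some stated number of severe reactions, are lost. The 140 is an upper bound on non-randomized children, and the number of omitted events cannot be derived from the documents.

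The primary endpoint and the drug-safety comparison between arms are unaffected.

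**What to change.** In SAP 3.2, 4.6 and 4.9.10, tabulate and list entry-challenge SAEs for all screened children who took at least one entry-challenge dose, with non-randomized children in a separate column. Do the same for symptom severity and epinephrine use where they were captured. Name this population in the SAE sentence of 4.9.10.

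Keep the Safety population for Month 12 and for change by arm. Adding screen failures cannot repair the change score, so footnote it: the entry values exclude children barred by exclusion 3 and children who did not react at 300 mg or below.

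The cost is SAP wording, one extra column and some programming. Screening SAEs are already in the e-CRF, and Protocol 9.2.1 asks for the e-CRF to be completed for every consented child, so the challenge pages should exist. If they were not completed for screen failures, the added column is limited to SAEs and the table should say so.
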